Name of company:		Boehringer Ingelheim	
Name of finished prod	uct:	NA	
Name of active ingredi	ent:	BI 695501	
Protocol date: 30 May 2016	Trial number: 1297.4		Revision date: 12 Dec 2017
Safety criteria:	assessment, physical	include continuous AE mor l examination, vital signs (blood st (IGRA), 12-lead ECG, injectio	l pressure, pulse rate, and body
Statistical methods:	 BI 695501 with EU- The statistical mode binomial regression exposure to inflixim as fixed, categorical For the primary and endpoints) together interpreted in a desc. The safety population partial) dose of either of AEs will be based AEs with an onset a 	secondary endpoints, point estir with their 90% and 95% CIs	th active Crohn's disease. y endpoint will be a log-linked the stratification factors (prior CD [<16 or \geq 16]) and treatment mates (risk difference for binary will be calculated, but will be tho receive at least one (full or any dosing period. The analysis ergent AEs. That means that all tion up to a period of 10 weeks

09542349-05Trial ProtocolPage 7 of 93Proprietary confidential information © 2017 Boehringer Ingelheim International GmbH or one or more of its affiliated companies

Name of company:		Boehringer Ingelheim	
Name of finished product:	:	NA	
Name of active ingredient	:	BI 695501	
Protocol date:	Trial number:		Revision date:
30 May 2016	1297.4		12 Dec 2017
	will also be considere appropriate trial phas	start before first drug intake and de ed as treatment-emergent. Other Al ses, i.e., screening or post-treatme ted descriptively; in addition RR ar presented.	Es will be assigned to the nt. Safety endpoints and

09542349-05Trial ProtocolPage 8 of 93Proprietary confidential information © 2017 Boehringer Ingelheim International GmbH or one or more of its affiliated companies

FLOW CHART A: SCREENING AND INDUCTION PERIOD

Trial Period	Screen	ing	In	duction		EoT ²	SFU ²
Visit	1	1.1	2 ¹	3	4		
Week	-4 to -2	-1	-1 0 2 4		4	-	14
Day	-28 to -14	-9	1	15	29	-	99
Permitted visit window (days)	-	±2	-1/+2	±1	±1	±3	+7
Informed consent	Х						
Assessment of eligibility	Х	Х	Х				
Demographics	Х						
Medical and surgical history, incl. history of opportunistic infection	Х						
LABS/SAFETY ASSESSMENT	ſS						
Infection screen: hepatitis B							
(HBsAg), hepatitis C (antiHCV), and HIV test (where mandated by local authorities)	Х						
Chest X-ray ³	Х						
TB testing (IGRA) ⁴	X					Х	
CRP/fecal calprotectin	X		X		X	X	
Pregnancy test ⁵	Х		X			Х	Х

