5.1 TRIAL ENDPOINTS

5.1.1 **Primary Endpoint(s)**

The primary endpoint is:

• Proportion of patients in each treatment group with a clinical response (CDAI decrease of ≥70 compared with baseline) at Week 4

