7.7 DETERMINATION OF SAMPLE SIZE

The sample size determination is not based on a power calculation, but assures a precise estimation of the relative risk difference. For this trial a precision (distance from observed difference to confidence limit) of 0.115 has been considered necessary and sufficient by the project team. Assuming a response rate of 80%, in both the Humira as well in the BI 695501 treatment arm, the trial will need at least 130 patients (65 per treatment arm).

Page 68 of 93

Proprietary confidential information © 2017 Boehringer Ingelheim International GmbH or one or more of its affiliated companies

Table 7.7: 1Precision of 90% CI

Assumed true response rate		Sample size	Precision ^{\$}	Relative risk (RR)	90% CI
Humira	BI 695501				
85%	85%	65	0.103	1	0.897-1.103
85%	80%	65	0.118	0.941	0.823-1.059
85%	75%	65	0.115	0.882	0.767-0.997
80%	80%	65	0.115	1	0.885-1.115
80%	75%	65	0.120	0.938	0.818-1.058
75%	75%	65	0.125	1	0.875-1.125

⁵Precision is defined as the distance from observed difference to confidence limit. Note that the precision is independent of the actual point estimate.

Calculations performed with nQuery Advisor® 7.0

Table 7.7: 2Precision of 95% CI

Assumed true response rate		Sample size	Precision ⁸	Relative risk (RR)	95% CI
Humira	BI 695501				
85%	85%	65	0.123	1	0.877-1.123
85%	80%	65	0.140	0.941	0.801-1.081
85%	75%	65	0.136	0.882	0.746-1.081
80%	80%	65	0.138	1	0.862-1.138
80%	75%	65	0.143	0.938	0.795-1.081
75%	75%	65	0.149	1	0.851-1.149

^{\$}Precision is defined as the distance from observed difference to confidence limit. Note that the precision is independent of the actual point estimate.

Calculations performed with nQuery Advisor[®] 7.0

Page 69 of 93

Proprietary confidential information © 2017 Boehringer Ingelheim International GmbH or one or more of its affiliated companies

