3.3. CHANGES TO ANALYSIS FROM PROTOCOL

No change to analysis from protocol is planned.

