15.1.3. PRIMARY ANALYSIS OF PRIMARY EFFICACY VARIABLE

The primary efficacy analysis will be performed for the FAS. Patients will be assigned to the treatment they were randomized to receive.

The primary objective of this trial is to compare the clinical efficacy of BI 695501 with EU-approved Humira in patients with active CD at the end of the induction phase at Week 4 by means of the Relative Risk (RR).

The primary analysis of the observed proportion of patients with a clinical response (CDAI decrease of ≥ 70 compared with baseline) at Week 4 will be based on log-linked binomial model.

The statistical model can be described as follows:

- (M1) Response to treatment at Week 4 = treatment + prior infliximab exposure + screening SES-CD

This model includes the stratification factor, prior exposure to infliximab, and treatment as fixed effects and screening SES-CD will be included as a categorical effect:

- Treatment (BI 695501, EU-approved Humira)
- Prior exposure to infliximab (Yes/No)
- Screening SES-CD (< 16 or ≥ 16)

The relative risk estimate together with its 90% and 95% CI (ratio scale) will be produced. The following SAS code will be used:

```
proc genmod data=data_CDAI70 descend;  
  class CDAI70 (ref="N") TRTP (ref="HUMIRA") EXP_PRIO (ref="N") BAS_SES  
    (ref="<16") / param=GLM;  
  model CDAI70=TRTP EXP_PRIO SCR_SES / dist=binomial link=logit;  
  lsmeans TRT / ilink;
```

run;

Document: \\ieedc-
vnasc01\BIOSdata\Boehringer_Ingelheim\BI_695501\NVA96252\Biostatistics\Documentation\S
AP\BI1297.4 SAP FINAL v4.0_22MAY2019.docx

Author: Version Number: Final V4.0
Version Date: 22MAY2019

Template No: CS_TP_BS016 Revision 5 Reference: CS_WI_BS005
Effective Date: 01Apr2018

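### The synopsis promises a risk difference for the primary endpoint, but protocol 7.3.1 and SAP 15.1.3 specify only a relative risk, although the 0.115 precision behind N = 130 is on the risk-difference scale

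*SAP*

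**What the plan says.** The primary endpoint is binary (protocol 5.1.1): "Proportion of patients in each treatment group with a clinical response (CDAI decrease of ≥70 compared with baseline) at Week 4".

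The synopsis, under Statistical methods, has one sentence on estimates. It is broken across table lines in the copy read, but its parts are legible. Its scope opens with "For the primary and" and goes on to the secondary endpoints. The estimate is given in parentheses as "risk difference for binary" endpoints, to be shown "with their 90% and 95% CIs" and interpreted descriptively. The same synopsis section names a log-linked binomial regression for the primary endpoint.

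The body of the protocol differs. Section 7.1 frames the primary comparison as a relative risk (RR). Section 7.3.1 and SAP 15.1.3 give the same output sentence: "The relative risk estimate together with its 90% and 95% CI (ratio scale) will be produced". Neither section mentions a risk difference.

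Elsewhere a risk difference is specified:
- secondary efficacy endpoints: protocol 7.3.2.1, and SAP 15.2.1.1 and 15.2.1.2 (Week 24 response and remission, RR and risk difference, 90% and 95% CIs);
- adverse events: SAP 16.1.1.2 and 16.1.1.3 (RR and risk difference, 95% CIs only).

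Protocol 7.7 sets the sample size by a precision of 0.115 at 80% response in both arms with 65 per arm. The table footnote reads: "Precision is defined as the distance from observed difference to confidence limit". The tables nevertheless place that distance around an RR.

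**The concern.** The two parts of the protocol name different estimates for the primary endpoint, and the SAP follows only one of them. The amendment log does not explain this. Global Amendment 2 lists the synopsis statistical methods, 7.3.1, 7.3.2.1 and 7.7 as revised together, so the synopsis sentence is current text.

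Two things are at stake. The trial is exploratory and its sample size rests on precision alone, so the report should be able to show the precision reached on the scale used to plan it. Also, an RR does not convey the absolute loss of response unless the comparator rate is known, and the protocol itself contains two quite different rates: 80% (7.7) and a pooled historical 54.1% (Appendix 10.3).

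**Working it through.** **Inputs.** Response 80% in both arms, 65 per arm, target 0.115 (protocol 7.7); the tabulated rates and precisions (Tables 7.7: 1 and 7.7: 2); pooled historical rate 54.1% (Appendix 10.3); exploratory RR margin 0.76 (7.3.1). All calculations are unadjusted.

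**1. Reproduce the plan's figure as a risk difference.** Half-width = z × √[p₁(1−p₁)/n + p₂(1−p₂)/n].
- At 80%/80%, n = 65: √(2 × 0.8 × 0.2/65) = 0.0702.
- 90%: 1.645 × 0.0702 = 0.1154 (stated 0.115).
- 95%: 1.960 × 0.0702 = 0.1375 (stated 0.138).
- Solving for n at 0.115: 2 × 0.16 × (1.645/0.115)² = 65.5 per arm (stated 65).

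**2. Check the other rows (Humira/BI 695501).**

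| Rates | Stated 90% | Computed | Stated 95% | Computed |
|---|---|---|---|---|
| 85/85 | 0.103 | 0.1030 | 0.123 | 0.1228 |
| 85/80 | 0.118 | 0.1094 | 0.140 | 0.1303 |
| 85/75 | 0.115 | 0.1145 | 0.136 | 0.1364 |
| 80/80 | 0.115 | 0.1154 | 0.138 | 0.1375 |
| 80/75 | 0.120 | 0.1203 | 0.143 | 0.1433 |
| 75/75 | 0.125 | 0.1249 | 0.149 | 0.1489 |

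Five of six rows match the risk-difference formula in each table. The exception is 85/80.

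**3. Try the RR scale.** The standard error of log RR at 80%/80% is √[2 × 0.2/(65 × 0.8)] = 0.0877.
- 90% CI: exp(±1.645 × 0.0877) = 0.866 to 1.155. The table prints 0.885 to 1.115.
- 95% CI: exp(±1.960 × 0.0877) = 0.842 to 1.188. The table prints 0.862 to 1.138.
- The delta-method 90% half-width for the RR is 0.144, not 0.115.
- A 90% lower RR limit of 0.885 would need 0.5 × (1.645/ln(1/0.885))² = 90.6, that is 91 per arm.

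So 0.115 is a risk-difference half-width that has been set around an RR of 1.

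**4. Dependence on the response rate.**
- RR 0.90: 0.80 × 0.10 = 8.0 points lost at 80%; 0.541 × 0.10 = 5.4 points at 54.1%.
- RR 0.76: 0.80 × 0.24 = 19.2 points; 0.541 × 0.24 = 13.0 points.
- At 54.1% in both arms the risk-difference half-width is z × √(2 × 0.541 × 0.459/65) = 0.144 (90%) and 0.171 (95%). Whether 0.115 is reached therefore depends on the rate observed.

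**The case against.** The best answer is that the RR is the intended primary measure throughout: in protocol 7.1, in 7.3.1 and its 0.76 hypotheses, in SAP 15.1.3, and in the log-linked model that the synopsis itself names. On that view the risk difference is a loose parenthesis covering two classes of endpoint at once, and correcting the synopsis would end the matter. This stands as far as it goes. The RR is the primary measure, and a synopsis correction is a legitimate repair. It would not repair Table 7.7, which is on the other scale.

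It can also be said that little is lost. The endpoint is a proportion per arm, the SAP code requests per-arm probabilities, and disposition reports Week 4 responders. The absolute difference follows by subtraction, and an unadjusted interval could be computed from counts. That also stands: what is missing is a prespecified estimate with its interval and method. No decision rule depends on it, because the trial has no confirmatory hypothesis.

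A reader might infer three stronger things that the documents do not support:
- *That a primary estimate will never be computed.* The table templates are not available and parts of the SAP are blank, so one can say only that no visible text specifies it.
- *That the primary endpoint is the only binary comparison without an absolute effect.* This cannot be shown for the same reason, and the Hy's law and DILI laboratory proportions in SAP 16.3 have no risk difference of their own.
- *That SAP 3.3 is false in stating* "No change to analysis from protocol is planned". SAP 15.1.3 repeats the output sentence of protocol 7.3.1. The mismatch lies inside the protocol, between synopsis and body.

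**Conclusion.** The concern holds as an inconsistency within the protocol that the SAP carries forward. The synopsis assigns a risk difference with 90% and 95% CIs to the primary endpoint, while protocol 7.3.1 and SAP 15.1.3 specify an RR only. It is more than an editorial matter because the sample size was justified by the precision of the estimate left out: 0.1154 on the risk-difference scale, against an RR interval of 0.866 to 1.155 for the same design. The specified primary output does not show whether 0.115 was achieved.

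The size is moderate. N does not change, the RR remains the primary measure, and no formal conclusion turns on the missing estimate. The figures assume 65 analysed patients per arm, the rates in Table 7.7 and no covariate adjustment.

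A related point is separate from this one: the code in SAP 15.1.3 uses a logit link, so as written it yields neither an RR nor a risk difference with its interval. Adding a risk difference would not cure that.

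**What to change.** Keep the RR as the primary measure. Add to protocol 7.3.1 and SAP 15.1.3 a sentence such as: *The risk difference in Week 4 response will be presented with 90% and 95% CIs on the FAS, and on the PPS as a sensitivity analysis, by a prespecified method that accounts for prior infliximab exposure and screening SES-CD (<16 or ≥16).* Mantel-Haenszel weights are one suitable method. The documents do not call for any particular one, but the choice should be written down. State in Tables 7.7: 1 and 7.7: 2 that the precision is on the risk-difference scale, show the intervals around the difference, and check the 85/80 row.

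If the sponsor intends the RR only, the alternative is to correct the synopsis to say so for the primary endpoint and to recompute Table 7.7 on the RR scale. The 80/80 row would then read 0.866 to 1.155 at 90%, and the stated precision would have to be restated.

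The cost of the first route is one sentence in each document, a relabelled table, one extra row in the primary results and a second descriptive estimate to interpret. It needs no new data and no change in N.

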7. STATISTICAL METHODS AND DETERMINATION OF SAMPLE SIZE

7.1 STATISTICAL DESIGN - MODEL

This is a randomized, double-blind, parallel arm, multiple dose, multicenter, multinational, active comparator trial of BI 695501 and EU-approved Humira.

The primary objective of this trial is to compare the clinical efficacy of BI 695501 with EU-approved Humira in patients with active CD at the end of the induction phase at Week 4 by means of the RR.

The primary endpoint (Section 5.1.1) will be analyzed using a log-linked binomial model, which will include stratification factors as covariates (i.e., prior exposure to infliximab [yes/no] and screening SES-CD (<16 or \geq 16).

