7.3.1 Primary endpoint analyses

Primary efficacy analysis:

The primary analyses will be performed on the FAS. Patients will be assigned to the treatment they were randomized to receive.

The primary analysis of the observed proportion of patients with a clinical response (CDAI decrease of \geq 70 compared with baseline) at Week 4 will be based on log-linked binomial model. No missing data imputation for primary analysis endpoint need to be taken into account due to FAS definition. However, for pre-specified criteria non-responder imputation (NRI) will be applied (see Section 7.5).

The statistical model can be described as follows:

• (M1) Response to treatment at Week 4 = treatment + prior infliximab exposure + screening SES-CD

This model includes the stratification factor, prior exposure to infliximab, and treatment as fixed, categorical effects and it will be investigated whether the baseline SES-CD will be included as a continuous or as a categorical effect:

- Treatment (BI 695501, EU-approved Humira)
- Prior exposure to infliximab (Yes/No)
- Baseline SES-CD ($<16 \text{ or } \ge 16$)

The relative risk estimate together with its 90% and 95% CI (ratio scale) will be produced.

Further efficacy analyses:

As sensitivity analyses to the primary analysis, the primary endpoint will also be analyzed on the PPS with NRI.

The following explorative hypotheses are not intended to support any biosimilarity claim for BI 695501; however, the framework of non-inferiority testing will be used to compare efficacy of BI 695501 versus EU-approved Humira in a descriptive way.

The following hypotheses will be investigated:

- H_0 : RR of proportion of patients with a clinical response (CDAI decrease of \geq 70 compared with baseline) at Week 4 (BI 695501 versus EU-approved Humira) is less than or equal to 0.76
- H₁: RR of proportion of patients with a clinical response (CDAI decrease of ≥70 compared with baseline) at Week 4 (BI 695501 versus EU-approved Humira) is greater than 0.76

Two-sided 90% CI will be used for the comparison.

The applied margin (0.76 on the ratio scale for CDAI 70) does preserve 39% of the historical effect of adalimumab over placebo (based on a meta-analysis of GAIN and CLASSIC1; see Appendix 10.3 for further details).

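### The SAP's code for the primary analysis fits a logit link and requests no treatment comparison, so it cannot give the relative risk and CIs that both documents specify

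*SAP*

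**What the plan says.** The prose is consistent across the two documents. Protocol 7.1 says the primary endpoint "will be analyzed using a log-linked binomial model" with the stratification factors as covariates. Protocol 7.3.1 adds: "The relative risk estimate together with its 90% and 95% CI (ratio scale) will be produced". SAP 15.1.3 repeats this: the analysis of Week 4 response "will be based on log-linked binomial model", the objective is a comparison by means of the RR, and both intervals are to be given on the ratio scale. It also settles that screening SES-CD (<16 or ≥16) enters as a categorical effect. SAP 3.3 declares no change from the protocol's analysis.

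SAP 15.1.3 then states "The following SAS code will be used" and prints a GENMOD step. Its model line is "model CDAI70=TRTP EXP_PRIO SCR_SES / dist=binomial link=logit" and its only post-fit statement is "lsmeans TRT / ilink". The CLASS statement lists CDAI70, TRTP, EXP_PRIO and BAS_SES.

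**The concern.** The text and the code in the same SAP section describe different models. The code is presented as what will be run, and it is the only code shown for the primary endpoint. Run as intended, it would not deliver the primary estimate.

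Two things are at stake. First, someone will have to rewrite the link, the contrast and the covariate coding before the result can be produced. If that happens when the unblinded snapshot is analysed, those choices were not settled in advance. Second, the treatment effect that a logit fit does print, once exponentiated, is an odds ratio. At response rates between 54% and 85% this is far from the RR, and it cannot be set against the RR margin of 0.76 in Protocol 7.3.1.

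**Working it through.** **1. Text against code**

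| Element | Text (Protocol 7.1 and 7.3.1, SAP 15.1.3) | Code (SAP 15.1.3) |
|---|---|---|
| Link | log | `link=logit` |
| Treatment effect | RR | coefficient is a log odds ratio |
| Comparison of arms | RR, BI 695501 to Humira | `ilink` only; no DIFF, EXP or ESTIMATE |
| Intervals | 90% and 95% | no CL or ALPHA option |
| Treatment variable | one factor | TRTP in MODEL, TRT in LSMEANS |
| Screening SES-CD | categorical (SAP) | BAS_SES in CLASS, SCR_SES in MODEL |

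The `ilink` option returns one predicted response probability per arm. A ratio of the two could be formed by hand, but the code does not form it and gives it no interval, and it would not be the log-binomial estimate.

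The effect of the SES-CD mismatch depends on how SCR_SES is stored, which the documents do not say. A numeric two-level code would leave the treatment estimate unchanged, a character variable should stop the program, and a raw score would be fitted as a linear term.

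**2. Inputs for the size of the gap**

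- 65 patients per arm, and response rates of 75% to 85% (Protocol 7.7 and its tables)
- Pooled historical response rate 54.1% (Protocol Appendix 10.3)
- Margin RR 0.76, compared with a two-sided 90% CI (Protocol 7.3.1)

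**3. The plan's own figure**

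Protocol 7.7 states a 90% precision of 0.115 at 80% in both arms. The half-width of the risk difference is 1.645 × √(2 × 0.8 × 0.2 / 65) = 1.645 × 0.0702 = 0.1154, which agrees. This confirms the inputs. It is on the difference scale, so it checks neither ratio below.

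**4. RR and OR on the same data**

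Unadjusted Wald intervals on the log scale, with *p*B for BI 695501 and *p*H for Humira:

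- SE(log RR) = √[(1−*p*B)/(65 *p*B) + (1−*p*H)/(65 *p*H)]
- SE(log OR) = √[1/(65 *p*B(1−*p*B)) + 1/(65 *p*H(1−*p*H))]
- 90% limits: estimate × exp(±1.645 × SE)

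Worked case, Humira 80% and BI 695501 75%:

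- RR = 0.75/0.80 = 0.938. SE = √(0.25/48.75 + 0.20/52) = √0.008974 = 0.0947. Limits 0.9375 × exp(±0.1558) = 0.802 to 1.096.
- OR = (0.75/0.25)/(0.80/0.20) = 0.750. SE = √(1/12.1875 + 1/10.4) = √0.1782 = 0.4221. Limits 0.75 × exp(±0.6944) = 0.375 to 1.502.

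| Humira / BI 695501 | RR (90% CI) | OR (90% CI) |
|---|---|---|
| 80% / 80% | 1.000 (0.866–1.155) | 1.000 (0.486–2.057) |
| 80% / 75% | 0.938 (0.802–1.096) | 0.750 (0.375–1.502) |
| 85% / 75% | 0.882 (0.763–1.021) | 0.529 (0.252–1.110) |
| 54.1% / 54.1% | 1.000 (0.767–1.304) | 1.000 (0.560–1.784) |
| 54.1% / 50% (50% assumed) | 0.924 (0.700–1.220) | 0.848 (0.476–1.512) |

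In the first four rows the lower RR limit is above 0.76 and the lower OR limit is below it. In the last row both are below, so the reading against the margin does not always reverse.

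**The case against.** The strongest reply is that this is a coding slip which the documents themselves resolve. The model, effect measure and interval levels are stated correctly and consistently in prose. Because LSMEANS names an effect that is not in the model, the step cannot run as intended, so a programmer must revisit it anyway and will find the right specification a few lines above. Reporting an odds ratio as an RR would mean mislabelling output that the SAP calls a relative risk. The trial is exploratory, Protocol 7.2 defines no confirmatory hypotheses, and Protocol 7.3.1 uses 0.76 descriptively only. The SAP's output templates, which are not available here, may show the intended RR table.

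Much of this stands as a limit on the consequences. No formal decision rule fails, and the harm from misreading an OR is possible, not certain. It is also fair that GENMOD's default parameter table would show a BI 695501 versus Humira coefficient, so a comparison does appear implicitly, but as a log odds ratio with a 95% interval only.

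None of it repairs the code. The SAP says this code will be used, and no other available section gives a method for the primary RR. A template cannot turn a logit fit into a log-binomial one. Nor is it a single typing error: the link, the missing contrast and intervals, and two variable-name mismatches all need correction. The SAP's adverse-event code in 16.1.1.2, by contrast, requests a relative risk.

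**Conclusion.** The concern holds. As printed, the code for the primary endpoint does not fit the specified model and produces neither the RR nor a 90% CI. This follows from reading the text against the code and needs no numerical assumption.

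If the logit coefficient were exponentiated and read as the RR, the error would be large. At 80% versus 75% the estimate would be 0.750 in place of 0.938, and at 80% in both arms the lower 90% limit would be 0.486 in place of 0.866. These figures assume 65 analysed patients per arm and the protocol's response rates. They are unadjusted, because the documents give no stratum prevalences, so adjusted values will differ somewhat. The conclusion is limited to the code shown in the SAP. Although the trial is exploratory, this is its primary analysis and should be corrected before the code is run on unblinded data.

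**What to change.** Amend the code in SAP 15.1.3 to match its text:

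- fit `dist=binomial link=log`;
- use the same names throughout: TRTP, EXP_PRIO and SCR_SES in both CLASS and MODEL, with SCR_SES defined as the <16 / ≥16 category;
- replace the LSMEANS line with `lsmeans TRTP / diff=control('HUMIRA') exp cl alpha=0.10`, and repeat at `alpha=0.05`, so that the exponentiated difference is the RR of BI 695501 to Humira with each interval.

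A useful addition, though separate from the error itself, is to name one fallback in case the log-binomial fit does not converge, which is a risk at response rates near 80%. Modified Poisson regression with a log link and robust variance keeps the RR as the estimate.

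The cost is a few lines of SAP text. No data collection, patient burden or sample size is affected.
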